## Group B: placebo

### Treatment Period 1

- Placebo (1 × 1.0 mL PFS) at Baseline, Week 1, 2, 3 and 4

### Treatment Period 2

Patients randomized to placebo at Baseline will be re-randomized to secukinumab 150 mg or 300 mg at Week 8:

- **Arm B1:** secukinumab 150 mg (1 × 1.0 mL PFS) + placebo (1 × 1.0 mL PFS) administered every 4 weeks from Week 8 to Week 20
- **Arm B2:** secukinumab 300 mg (2 × 1.0 mL PFS) administered every 4 weeks from Week 8 to Week 20

Patients will be allowed to continue background medications in accordance with concomitant medication and prohibited medication (Section 5.5.7 and Section 5.5.8).

## 5.3 Treatment assignment and randomization

At Baseline, all eligible patients will be randomized to one of the treatment groups (Group A and Group B) via an Interactive Response Technology (IRT) system or similar system. The investigator or his/her delegate will contact the IRT after confirming that the patient fulfills all the inclusion/exclusion criteria. The IRT will assign a randomization number to the patient, which will be used to link the patient to a treatment group and will specify a unique medication number for the first package of study drug to be dispensed to the patient. The randomization number will not be communicated to the caller.

Randomization at Baseline will be stratified based on prior TNF $\alpha$  inhibitor exposure (i.e. according to whether patients are TNF $\alpha$  inhibitor naïve or TNF $\alpha$ -IR). It is assumed that approximately one third of the randomized patients will be TNF $\alpha$ -IR.

At Week 8, patients randomized to Group A (secukinumab 150 mg) at Baseline will be assessed for the achievement of spinal pain NRS score and will be classified as responders (spinal pain NRS score  $< 4$ ) or non-responders (spinal pain NRS score  $\geq 4$ ) and re-randomized or re-assigned via IRT to one of the treatment arms (Arm A1, Arm A2, Arm A3) as outlined in Section 5.2. At Week 8, patients randomized to Group B (placebo) at Baseline will be re-randomized via IRT to one of the 2 treatment arms (Arm B1 or Arm B2) as outlined in Section 5.2.

The IRT will be used to link the patient to a treatment group/arm and will specify unique medication numbers for the study drug to be dispensed to the patient. The randomization

numbers will not be communicated to the caller and will be generated using the following procedure to ensure that treatment assignment is unbiased and concealed from patients and investigator staff. A patient randomization list will be generated in collaboration with the IRT provider using a validated system that automates the random assignment of patient numbers to randomization numbers. These randomization numbers are linked to the different treatment groups/arms, which are in turn linked to medication numbers. A separate medication list will be produced in collaboration with Novartis Drug Supply Management using a validated system that automates the random assignment of medication numbers to packs containing the investigational drugs.

The randomization scheme for patients will be reviewed and endorsed by a statistical expert.

#### **5.4 Treatment blinding**

Patients, investigator staff, persons performing the assessments, and data analysts will remain blind to the identity of the treatment from the time of randomization until database lock using the following methods:

- Randomization data are kept strictly confidential until the time of unblinding, and will not be accessible by anyone else involved in the study.
- The identity of the treatments will be concealed by the use of study drug that are all identical in packaging, labeling, schedule of administration, appearance, taste and odor.

Unblinding will only occur in the case of patient emergencies (see Section 5.5.9) and at the conclusion of the study.

#### **5.5 Treating the patient**

Sponsor qualified medical personnel will be readily available to advise on trial related medical questions or problems.

##### **5.5.1 Patient numbering**

Each patient is uniquely identified by a Patient Number which is composed of the site number assigned by Novartis and a sequential number assigned by the investigator. Once assigned to a patient, the Patient Number will not be re-used.

Upon signing the informed consent form (ICF), the patient will be assigned the next sequential number by the investigator. The investigator or his/her staff will contact the IRT and provide the requested identifying information for the patient to register them into the IRT. The site must select the case report form (CRF) book with a matching Patient Number from the electronic data capture (EDC) system to enter data.

If the patient fails to be treated for any reason, the IRT must be notified within 2 days that the patient was not treated. The reason for not being treated will be entered on the Screening Period Study Disposition electronic CRF.

##### **5.5.2 Dispensing the study drug**

Each study site will be supplied with study drug in packaging of identical appearance.

The study drug packaging has a 2-part label. A unique medication number is printed on each part of this label, which corresponds to placebo or active treatment. Investigator staff will identify the study drug packages to dispense to the patient by contacting the IRT and obtaining the medication numbers. Immediately before dispensing the packages to the patient, investigator staff will detach the outer parts of the labels from the packages and affix them to the source document (Drug Label Form) for that patient's unique Patient Number.

At Week 12, the investigator will dispense to the patient, supported by IRT, 2 study drug packages for home administrations at Week 16 (see [Table 6-1](#)). The investigator will detach the outer parts of the labels and affix them to the source documentation (Drug Label Page). Detailed instructions on the self-administration of the study treatment will be described in the Instructions for Use (IFU) provided to each patient and made available to the site staff and investigator. These instructions should be reviewed in detail by the patient and the site personnel.

### **5.5.3 Handling of study and additional treatment**

#### **5.5.3.1 Handling of study treatment**

The study treatment must be received by a designated person at the study site, handled and stored safely and properly, and kept in a secured location to which only the investigator and designees have access. Upon receipt, all study treatment must be stored according to the instructions specified on the labels. Clinical supplies are to be dispensed only in accordance with the protocol. The investigator should educate the patient on how to properly store the study treatment when the patient is self-administering at home. Technical complaints are to be reported to the respective Novartis Country Pharma Organization (CPO) Quality Assurance or trial assigned Quality Assurance function.

The PFSs, which are sealed in their outer box, must be stored in a locked refrigerator between 2°C and 8°C (36°F and 46°F) and must be carefully controlled in accordance with regulations governing investigational medicinal products, local regulations and in accordance with instructions from the Novartis Drug Supply Management or Novartis Drug Supply Chain or corresponding service providers. The study drug should be protected from light and must not be frozen.

Medication labels will be in the local language and comply with the legal requirements of each country. They will include storage conditions for the study treatment but no information about the patient except for the medication number.

The investigator must maintain an accurate record of the shipment and dispensing of study treatment in a drug accountability log. Monitoring of drug accountability will be performed by monitors during site visits or remotely and at the completion of the trial. Patients will be asked to return all unused study treatment and packaging at the end of the study or at the time of discontinuation of study treatment.

At the conclusion of the study, and as appropriate during the course of the study, the investigator will return all unused study treatment, packaging, drug labels, and a copy of the completed drug accountability log to the Novartis monitor or to the Novartis address provided in the investigator folder at each site.

### **5.5.3.2 Handling of other study treatment**

Not applicable.

### **5.5.4 Instructions for prescribing and taking study treatment**

Patients will self-administer the study treatment (secukinumab 150 mg, secukinumab 300 mg and placebo) by s.c. injection using 1 mL PFSs throughout the study. The dosing frequency will be either weekly or every 4 weeks in accordance with the administration schedule ([Table 6-1](#) and [Table 6-2](#)).

Patients will receive instructions and training from study center staff on how to self-administer the study drug. Detailed instructions on the self-administration of the study treatment will be described in the IFU for secukinumab and provided to each patient. Patients will be asked to raise any questions and then to proceed with self-injection.

The injections scheduled to occur at the study center (i.e. Baseline, Week 1, Week 2, Week 3 and Week 4 during Treatment Period 1, and Week 8, Week 12 and Week 20 during Treatment Period 2) will be done by the patient (or caregiver) at the study center, under the supervision of the investigator or study staff.

The injection not scheduled to occur during a study center visit (i.e. Week 16 injection) will be done by eligible patients (or caregiver) at their home.

All doses prescribed and dispensed to the patient during the study must be recorded in the electronic CRF (eCRF).

Patients will be asked to document all doses and dates of self-administration at home in a self-administration log and are required to return this log to the study center at the visit following home administration (i.e. Visit 9/Week 20).

The investigator should promote compliance by instructing the patient to attend the study visits as scheduled and by stating that compliance is necessary for the patient's safety and the validity of the study. The patient should be instructed to contact the investigator if he/she is unable for any reason to attend a study visit as scheduled or if he/she is unable for any reason to take the study treatment as prescribed.

At the beginning of the study, the investigator/qualified study center staff will determine if self-administration is appropriate for the patient, e.g. manual dexterity, ability to follow the secukinumab PFS-IFU. If a patient requires a caregiver to administer study drug, the caregiver should be trained by the investigator/qualified study center staff. If a caregiver is not available at a particular visit or the patient is having problems with self-administration, the investigator/qualified study center staff may administer the study drug to the patient. However, all patients should be trained sufficiently and be comfortable with the study drug self-administration before the first home administration visit. Patients will be instructed to contact the investigator site staff in case of any issue during home administration of the study treatment.

Records of study drug kits assigned to the patient during the study must be documented.

At each visit, all study assessments, including the completion of PROs, should be completed prior to self-injection of the study drug.

Prior to and following self-administration at home, patients should contact the investigator/site staff in case they are experiencing any AEs, SAEs, or have any concerns.

### **5.5.5 Permitted dose adjustments and interruptions of study treatment**

Study treatment dose adjustments are not permitted. Study treatment interruption is also not permitted with the following exceptions:

Study treatment interruption is permitted if, in the opinion of the investigator, a patient is deemed to be at a significant safety risk unless dosing is temporarily interrupted. In such cases study treatment should be interrupted only during the time that this risk is present and ongoing. Study treatment can be re-started after resolution of the safety risk. For additional points, please refer to Section 5.5.6.

Any study treatment interruption must be recorded on the corresponding eCRF page.

### **5.5.6 Allowed treatment modifications and escape treatment**

Treatment modifications as well as new therapeutic interventions or a significant change to ongoing therapy must not be made before completion of Week 8 assessments.

Although no patient will be restricted from receiving necessary medications for lack of benefit or worsening of disease, if treatment with prohibited biologics (as described in Section 5.5.8) occurs, patients may remain in the trial but must discontinue study treatment. Efficacy will be assessed in detail at every study visit, and patients who are deemed not to be benefiting from the study treatment based on safety and efficacy assessments or for any reason of their own accord will be free to discontinue participation in the study at any time (see Section 5.6.2).

As per Section 5.5.7, changes in non-biologic DMARDs and corticosteroids are permitted as per the investigator's clinical judgment after all Week 8 assessments are completed. However, it is recommended that these medications are continued at a stable dose from Week 8 through to Week 24. NSAIDs are to be administered in accordance with the posology and method of administration as described in the local Summary of Product Characteristics (SmPC).

Any treatment modifications or new therapeutic interventions must be recorded in the Concomitant medications eCRF page.

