### 5.5.8 Prohibited medication

Use of the treatments displayed in [Table 5-2](#) is not allowed after the start of the wash-out period unless otherwise specified below.

Patients who have previously been on a TNF $\alpha$  inhibitor will be allowed entry into the study after an appropriate wash-out period prior to randomization (see [Table 5-2](#)):

- 4 weeks for Enbrel® (etanercept) – with a terminal half-life of  $102 \pm 30$  hours (s.c. route)
- 8 weeks for Remicade® (infliximab) – with a terminal half-life of 8.0-9.5 days (i.v. infusion)
- 10 weeks for Humira® (adalimumab) – with a terminal half-life of 10-20 days (average 2 weeks) (s.c. route)
- 10 weeks for Simponi® (golimumab) – with a terminal half-life of 11-14 days (s.c. route)
- 10 weeks for Cimzia® (certolizumab) – with a terminal half-life of 14 days (s.c. route)

Live vaccines should not be given until 12 weeks after last study treatment administration.

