**Table 5-2 Prohibited medication**

Medication	Washout period (before randomization)
Etanercept*	4 weeks
Infliximab*	8 weeks
Adalimumab*	10 weeks
Golimumab*	10 weeks
Certolizumab*	10 weeks
Unstable dose of MTX or sulfasalazine	4 weeks
Conventional synthetic DMARDs other than MTX or sulfasalazine	4 weeks
Leflunomide	8 weeks
Leflunomide with cholestyramine wash-out	4 weeks
Targeted synthetic DMARDs (e.g. apremilast)	4 weeks
Systemic corticosteroids > 10 mg prednisone equivalent**	2 weeks
Intramuscular, intra-articular or intravenous corticosteroid treatment	4 weeks
Any biological immunomodulating agents, except those targeting TNF $\alpha$ *	No prior exposure
Any cell-depleting therapies including but not limited to anti-CD20 or investigational agents (e.g. Campath ® , anti-CD4, anti-CD5, anti-CD3, anti-CD19)	No prior exposure
Any investigational treatment or participation in any interventional trial	4 weeks or 5 half-lives (whichever is longer)
Analgesics other than NSAIDs or low strength opioids PRN, tramadol (refer to Section 5.5.7.2 for allowed doses of analgesics other than NSAIDs)	4 weeks
High strength opioids	4 weeks
Live vaccinations	6 weeks

CD=cluster of differentiation, COX1=cyclo-oxygenase 1, COX2=cyclo-oxygenase 1, DMARDs=disease-modifying anti-rheumatic drugs, MTX=methotrexate, NSAIDs=non-steroidal anti-inflammatory drugs, PRN=pro re nata (as needed), TNF $\alpha$ =tumor necrosis factor alpha

\* These agents fall under the category of biologic immunomodulators and are prohibited medications; administration of these agents requires study treatment discontinuation (see Section 5.6.2)

\*\* See details about corticosteroid management in Section 5.5.7.5

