### **5.6.2 Discontinuation of study treatment**

Discontinuation of study treatment for a patient occurs when study treatment is stopped earlier than the protocol planned duration, and can be initiated by either the patient or the investigator. If discontinuation occurs for any reason in a treatment period (i.e. Treatment Period 1 or 2), the investigator/qualified site staff must make every effort to determine the primary reason for the patient's discontinuation from the study. This information will then be recorded by the investigator/qualified site staff in the applicable eCRF section.

Study treatment must be discontinued if the investigator determines that continuation of study treatment would result in a significant safety risk for a patient.

The following circumstances require study treatment discontinuation:

- Withdrawal of informed consent
- Emergence of the following AEs:
  - a. Any severe AE or SAE that is not compatible with administration of study medication, including AEs that require treatment with prohibited co-medication
  - b. Onset of lymphoproliferative disease or any malignancy except for treated basal cell carcinoma, treated actinic keratoses, treated *in situ* carcinoma of the cervix or non-invasive malignant colon polyps, which are being or have been removed

- c. Life-threatening infection
- d. Severe hypersensitivity reaction or anaphylactic reaction
- e. Any laboratory abnormalities that in the judgment of the investigator are clinically significant and are deemed to place the patient at a safety risk for continuation in the study (general guidance on clinically notable laboratory values is provided in [Appendix 1](#))
- f. Pregnancy
- g. Use of any biologic immunomodulating agent except secukinumab

For patients who discontinue study treatment the CRF should be completed, giving the date and primary reason for stopping study treatment.

The investigator must also contact the IRT to register the patient's discontinuation from study treatment.

If study drug discontinuation occurs because the treatment code has been broken, please refer to Section [5.5.9](#).

Efficacy and safety will be assessed in detail at every study visit, and patients who are deemed not to be benefiting from the study treatment based upon safety and efficacy assessments by the investigator or for any reason on their own accord will be free to discontinue participation in the study at any time.

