EXCL23	Patients with any medical or psychiatric condition, which would preclude the participant from adhering to the study protocol.	INCLUDE IN EVERYTHING	0
EXCL24	Patients with history or evidence of ongoing alcohol or drug abuse within the last 6 months before randomization	INCLUDE IN EVERYTHING	0
EXCL25	Patients with administration of live vaccines 6 weeks prior to randomization or plans for administration of live vaccines during the study period	INCLUDE IN EVERYTHING	0
OTH01	Pregnancy test not performed as required per protocol	INCLUDE IN EVERYTHING	0
OTH02	Spinal pain NRS score at week 8 is missing.	INCLUDE IN EVERYTHING	0
OTH03	Spinal pain NRS score at baseline is missing	INCLUDE IN EVERYTHING	0

Deviation ID	Description of Deviation	Exclusion in Analyses	Severity code
OTH04	Patient PRO data was not collected according to the protocol	INCLUDE IN EVERYTHING	0
WITH01	Pregnant patient not withdrawn from study	INCLUDE IN EVERYTHING	0
WITH02	ICF withdrawn but patient continuing in the study	INCLUDE IN EVERYTHING	0
TRT01	Dosing error in comparative dosing phase (too many injections in treatment phase 1 and 2)	INCLUDE IN EVERYTHING	0
TRT02	Dosing error in comparative dosing phase (less than 2 injections in treatment phase 2)	INCLUDE IN EVERYTHING	0
TRT03	No study medication administered.	INCLUDE IN EVERYTHING	0
TRT04	Patient randomized mistakenly in the study and did not receive study drug.	EXCLUDE FROM FAS and SAF	3
TRT05	The patient was re-randomized to the wrong treatment arm.	INCLUDE IN EVERYTHING	0
TRT06	Patient was randomized to the wrong stratum at baseline.	INCLUDE IN EVERYTHING	0
TRT07	Study medication was administered, which could have been damaged.	INCLUDE IN EVERYTHING	0
COMD01	Prohibited medication consumed during study.	INCLUDE IN EVERYTHING	0
COMD02	Painkillers intake during 24h before a visit involving a disease activity assessment.	INCLUDE IN EVERYTHING	0

Table 2 Analysis set exclusions based on population codes

Analysis set	Population codes that cause a subject to be excluded
RAN	NA
SAF	2, 3
FAS	1, 3

Table 3 Population code text

Population Code	Population code text
0	INCLUDE IN EVERYTHING
1	EXCLUDE FROM FULL ANALYSIS SET (FAS)
2	EXCLUDE FROM SAFETY SET (SAF)

3

EXCLUDE FROM FAS AND SAF

6 Reference

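### After Week 8, Protocol 5.5.6 lets the investigator change a methotrexate or sulfasalazine dose while 5.5.8 with Table 5-2 still bars an unstable dose of either; corticosteroids are caught less clearly

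*Protocol*

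**What the plan says.** Protocol 5.5.6 forbids treatment modifications until the Week 8 assessments are complete. It then says, with a reference to 5.5.7, that "changes in non-biologic DMARDs and corticosteroids are permitted" at the investigator's judgement once those assessments are done. Staying on a stable dose to Week 24 is a recommendation there, and again in 5.5.7.3 (MTX), 5.5.7.4 (sulfasalazine) and 5.5.7.5 (corticosteroids). The daily corticosteroid maximum in 5.5.7.5 is tied to the interval from Baseline to Week 8.

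Protocol 5.5.8 says that use of the Table 5-2 treatments "is not allowed after the start of the wash-out period unless otherwise specified below". Table 5-2 includes "Unstable dose of MTX or sulfasalazine", "Conventional synthetic DMARDs other than MTX or sulfasalazine", leflunomide, targeted synthetic DMARDs, systemic corticosteroids above 10 mg prednisone equivalent, and "Intramuscular, intra-articular or intravenous corticosteroid treatment".

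On stopping study drug, the single-asterisk footnote to Table 5-2 and the text of 5.5.6 require it for biologics. Protocol 5.6.2(a) also requires it for a severe AE or SAE that is not compatible with study medication, "including AEs that require treatment with prohibited co-medication".

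SAP 5.5 has a deviation code, COMD01, for "Prohibited medication consumed during study". Patients with this code stay in every analysis set.

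**The concern.** A site that raises a patient's MTX dose at Week 12 follows 5.5.6 and breaches 5.5.8. Another site, reading 5.5.8 first, withholds the same change or reports it as a deviation. Protocol 5.5.7 asks that each concomitant drug be checked against the prohibited list and sets no Week 8 cut-off, so both sections are operative at the same moment.

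Three things depend on which section a site follows: the treatment the patient receives, whether COMD01 is recorded, and, in the limited case of 5.6.2(a), whether study drug must stop. The data affected are those of Treatment Period 2: maintenance and pain flares in Arm A1, A2 against A3, and B1 against B2.

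**Working it through.** This is a check of text. No stated figure depends on it. The sample size rests on Week 8 response only; the stated 332 (83 + 249) reproduces with the continuity-corrected two-proportion formula at 23.5% and 43.6%, 3:1 allocation, two-sided 5% and 90% power, and does not change.

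**Step 1: does 5.5.8 release anything after Week 8?** Its exception covers only what is specified below it. Below it stand the TNF inhibitor wash-out times, the live-vaccine sentence, and Table 5-2 with its footnotes. None mentions Week 8. Sections 5.5.6 and 5.5.7 stand above it, so on its own wording 5.5.8 is not qualified by them. The one pointer back that matters here is the double-asterisk footnote on systemic corticosteroids, which leads to 5.5.7.5. That section gives no limit after Week 8.

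**Step 2: how wide is the permission in 5.5.6?** Two readings are possible. Read through its reference to 5.5.7, and with 5.1.2, it covers MTX, sulfasalazine and systemic corticosteroids. Read without that reference, it covers all non-biologic DMARDs and all corticosteroids.

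| Table 5-2 row | 5.5.6 read through 5.5.7 | 5.5.6 read alone |
|---|---|---|
| Unstable MTX or sulfasalazine | Conflict, no footnote | Conflict |
| Systemic corticosteroids above the limit | Conflict, less clear (footnote to 5.5.7.5) | Conflict |
| Other conventional synthetic DMARDs | None | Conflict |
| Leflunomide | None | Conflict |
| Leflunomide with cholestyramine wash-out | None | Conflict |
| Targeted synthetic DMARDs | None | Conflict |
| Intramuscular, intra-articular or intravenous corticosteroids | None | Conflict |

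The count is one clear row and one less clear row on the first reading, and seven on the second. The first row conflicts on both. Continued stable MTX or sulfasalazine, and systemic corticosteroid changes within the table limit, do not conflict on either.

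**Step 3: does stopping study drug depend on it?** Not through the asterisk footnote or 5.5.6, which are limited to biologics. It does through 5.6.2(a), where the term used is prohibited co-medication without restriction to biologics. If a severe AE or SAE requires, say, a systemic corticosteroid above the table limit, that limb applies if Table 5-2 still holds and does not apply if 5.5.6 has lifted it.

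**Step 4: which analyses are exposed?** Changes are permitted only after the Week 8 assessments, so the primary and secondary endpoints precede them. COMD01 has population code 0. SAP 5.5 excludes codes 1 and 3 from the FAS and codes 2 and 3 from the safety set, so membership does not move. Data after Week 8 remain. At the planned rates, before dropout:

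- Arm A1: 264 × 0.436 = 115 patients.
- Group A non-responders: 264 × 0.564 = 149, so about 74 in each of A2 and A3.
- Group B: 88, so 44 in each of B1 and B2.

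The equal splits assume 1:1 re-randomization, a ratio that the protocol text does not state. These are the sizes of the groups, not the number of patients affected.

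**The case against.** The best defence is that Table 5-2 was meant as an entry rule. Its second column gives wash-out times before randomization, and the four-week row for unstable MTX or sulfasalazine mirrors the pre-randomization stability rules in 5.5.7.3 and 5.5.7.4. That may be the intention, but the opening sentence of 5.5.8 carries the list past the start of wash-out without an end.

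Second, 5.5.7 tells an investigator in doubt to contact the medical monitor before allowing a new medication. This helps, but a site relying on the permission in 5.5.6 has no reason to be in doubt, and a dose change is not a new medication.

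Third, the reference to 5.5.7 narrows 5.5.6. This stands. A reader might infer that every DMARD and corticosteroid row contradicts 5.5.6. The documents do not support that as the only reading: 5.1.2 names MTX, sulfasalazine and systemic corticosteroids, and 5.5.7.5 mentions injected corticosteroids only as a bar before randomization.

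Fourth, the effect on the comparisons is limited. Within A2 against A3 and B1 against B2, patients are re-randomized and blinded, so inconsistent reading by sites should add noise and is not expected to favour an arm. This also stands, though A1 is described without a randomized comparator and has no such protection. The Week 24 endpoints are exploratory and mainly descriptive.

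**Conclusion.** The contradiction is real for MTX and sulfasalazine dose changes after Week 8, arguable for systemic corticosteroids above the table limit, and dependent on a broad reading of 5.5.6 for the other rows. These are two operative rules with opposite answers, so the problem is more than missing detail.

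Its reach is modest. A reader might infer that patients in Treatment Period 2 are generally kept on or taken off study drug according to which section the site reads. The documents do not support this: outside biologics the only route is 5.6.2(a), which needs a severe AE or SAE requiring a drug still counted as prohibited. Nor is every one of the up to 352 patients exposed; only those who change or start one of these drugs after Week 8 are, and their number is not given. The effect on Week 24 rates therefore cannot be sized. The Week 8 results, their power and the analysis sets are unaffected. What remains is inconsistent site conduct, a COMD01 count that mixes two definitions, and uneven background therapy behind the exploratory Week 24 results.

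**What to change.** Reconcile the passages. For each DMARD and corticosteroid row of Table 5-2, state whether it applies before randomization only, up to Week 8, or throughout the study. Then make 5.5.6, 5.5.7.3 to 5.5.7.5, 5.6.2(a) and the definition of COMD01 in SAP 5.5 follow that list. Which rule is right is a clinical decision for the sponsor, and this review takes no position on it.

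Optionally, within the concomitant-medication tables already planned in SAP 2.4.2, show DMARD and corticosteroid changes made after Week 8 separately by Treatment Period 2 arm. This lets a reader of the Week 24 results see whether background therapy differed.

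The cost is one column in Table 5-2 and matching cross-references in a clarifying amendment, a line in the SAP for COMD01, and, if wanted, one further split of a planned table. The protocol already requires these doses and changes to be recorded in the eCRF, so no new data are needed. Sample size, endpoints and analysis sets stay as they are.
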